Automated DOT (a-DOT), a smartphone app that uses facial recognition software and advanced features to detect noningestion, combines the accuracy of in-person DOT with the convenience of real-time centralized data collection and monitoring. Adding a daily side effect diary to a-DOT will further allow precise tracking of timing of both medication ingestion and side effects which may be compromising adherence. Zepatier (elbasvir and grazoprevir) is a new once-daily fixe-dose combination tablet which has achieved high rates of SVR ranging from 94 to 97 percent in genotype-1 infected patients including those with HIV/HCV coinfection and renal impairment. Zepatier is administered for 12 to 16 weeks, depending on HCV genotype, prior treatment history, and the presence of certain baseline NS5A polymorphisms (1a only). By administering Zepatier via this innovative a-DOT platform, we hypothesize that PWIDs treated in real-wrold settings can be successfully treated with high rates of adherence and SVR.

In this proposed 18-month trials, 75 PWIDs enrolled in opiate agonist treatment (genotypes 1a and 1b) with chronic HCV will be enrolled over a 12-month period, and randomized to either aDOT or treatment as usual (TAU). **We will recruit PWIDs from diverse community settings include a syringe exchange program (NYHRE), federally-qualified health center (Comprehensive Health Care Center), homeless shelter (The Living Room), and a methadone maintenance treatment program (Montefiore Wellness Centers).** All patients (including treatment-experienced and HIVV/HCV coinfectd subjects) will be treated with Zepatier-based regimens as per the standard of care. Rigorous data are necessary to judge the contribution of a-DOT to the success of HCV treatment in PWIDs. By performing a randomized trial of a-DOT HCV therapy (Zepatier with and without ribavirin), we will evaluate the efficacy of a-DOT for improving HCV treatment outcomes among PWIDs.

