- 1. To determine in a randomized trial whether HCV treatment delivered via a-DOT (Zepatier with and without ribavirin) provided on-site at community treatment programs during a 12-week study period is more efficacious than self-administered HCV treatment for enhancing adherence and SVR in PWIDs.** 75 subjects will receive Zepatier will be randomized to take medications by either treatment as usual (self-administration), automated directly observed therapy (a-DOT), or a-DOT with gamification (25 subjects in each arm). Those in the a-DOT arm will be observed taking their Zepatier dose by the smart-phone based interface. We hypothesize that adherence and SVR will be higher in a-DOT versus TAU subjects, and that SVR in a-DOT arm will be equivalent to SVR seen in registration trials.
- 2. To evaluate the feasibility and acceptability of a-DOT to both participants and HCV providers in tracking longitudinal patterns of adherence and providing adherence feedback in real-time.** We hypothesize that a-DOT will be highly acceptable to both participants and medical providers.
- 3. To determine whether gaming features added to the aDOT platform enhance adherence compared to standard aDOT.** For the 25 subjects randomized to the aDOT + gamification arm, subjects will compete with other subjects within this arm for modest cash incentives. Those with highest levels of adherence measured at monthly research visits compared to their peers will earn additional incentives.

4. To determine the impact of ongoing drug use (cocaine, opiates, or benzodiazepenes) and on HCV virologic outcomes in subjects receiving Zepatier by aDOT. We hypothesize that ongoing drug use during HCV treatment will not be associated with adherence in subjects randomized to a-DOT.

B. APPROACH

B.1. Preliminary Studies

B.1.1. Overview of the research team. [name] has focused on defining optimal models of HCV care for PWIDs over the last 15 years, and is expert in treating HCV in PWIDs, methadone and buprenorphine-maintained patients, and active drug users.

Monitoring and improving adherence to antiviral therapy in real world settings requires methods that address varied challenges in treating high-risk populations. While accuracy is paramount, cost, ease of deployment, desirability, scalability, privacy, and flexibility are also important for ensuring wide-scale utility.

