In our previous DOT study, mean adherence in the mDOT group was 87% (SD=12%, n=21), and mean adherence in the TAU group was 77% (SD=20%, n=19) which translates into a standardized effect size or Cohen's d = 0.6. Based on this effect size, the power of the mixed effects linear model for the repeatedly measured continuous adherence outcome will be greater than 80%, even if anticipated ICC is as high as 0.5.

We will determine the proportion (and Wald or exact 95% CI) of subjects randomized to aDOT arm (n=50) who achieve SVR. For example, if SVR is achieved in 70% of the 50 study participants, the 95% confidence interval around that proportion will be: 57%, 83%. If SVR is achieved in 80%, the 95% confidence interval will be: 69%, 91%. If SVR is achieved in 90%, the 95% confidence interval will be: 82%, 98%. The overall SVR for all subjects will be compared to historical controls to demonstrate feasibility of treating real-world injection PWIDs with Zepatier-based regimens. Although our study lacks power to definitively answer the question of whether a-DOT improves SVR, our study will provide an estimated effect size to be used in future R01-funded studies examining the efficacy of a-DOT.

We used power calculations for Fisher's exact test (with 80% power and 5% significance level in a two-tailed test) to find the minimum detectable difference between the percentage of "adherent" subjects in the favorable group (e.g. not actively using drugs) vs. unfavorable group (e.g. actively using drugs). We would be able to find that a characteristic is significantly associated with adherence if there are 71% "adherent" subjects in the favorable group vs. no more than 41% "adherent" subjects in the unfavorable group (3.55 in terms of odds ratio). When using adherence as a continuous measure, we will have greater power to show correlations between continuous predictor variables and adherence. We calculated the minimum detectable correlation coefficient with 80% power and 5% significance level to be 0.33 which represents a small to medium correlation effect size. Therefore, we expect to have sufficient power to detect some associations that are likely to exist.

We will determine an effect size with respect to the outcome of adherence in the aDOT + gamification arm vs. a-DOT arm which will inform future R01 interventions.

C. References

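### Aim 1 predicts a-DOT SVR equivalent to registration-trial SVR, but the plan sets no margin, reference or criterion and never ties the planned a-DOT estimate (n=50) to that benchmark

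*Combined protocol and SAP*

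**What the plan says.** - Aim 1, in the numbered list of aims, predicts higher SVR with a-DOT than with TAU, and also that "SVR in a-DOT arm will be equivalent to SVR seen in registration trials".
- The opening summary gives the only SVR figures for Zepatier: "high rates of SVR ranging from 94 to 97 percent in genotype-1 infected patients". It does not label them as the reference for Aim 1.
- Aim 1 sets three arms, "25 subjects in each arm": TAU, a-DOT, and a-DOT with gamification.
- B.10 pools the two a-DOT arms for SVR: "We will determine the proportion (and Wald or exact 95% CI) of subjects randomized to aDOT arm (n=50) who achieve SVR". It works three examples at n=50. The one nearest the cited range reads "If SVR is achieved in 90%, the 95% confidence interval will be: 82%, 98" (per cent).
- B.10 then makes its only comparison with outside data: "The overall SVR for all subjects will be compared to historical controls to demonstrate feasibility". The historical controls are not identified, and no test or threshold is named.
- B.10 admits that the study lacks power on whether a-DOT improves SVR. It says nothing comparable about the registration-trial hypothesis.

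**The concern.** Equivalence can be concluded only against a stated reference and margin. Neither exists here, so the Aim 1 hypothesis has no matching analysis. The quantity it names, SVR under a-DOT, is estimated but set beside nothing. The quantity that is compared with outside data is a different one: it includes 25 TAU subjects, whom Aim 1 itself expects to do worse.

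What is at stake is the reporting. With 50 subjects the interval will be wide, and it may overlap 94–97% whether or not a-DOT truly matches that range. Without a rule fixed in advance, whether the result counts as equivalent would be decided after the data are seen. It would also depend on the interval chosen, because B.10 leaves Wald and exact both open.

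**Working it through.** **Inputs.** n=50 a-DOT subjects and 95% intervals (B.10); benchmark 94–97% (opening summary). The documents give no margin, so every margin below is my assumption. The benchmark is treated as a fixed number, and all 50 subjects are assumed to have an SVR result.

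**1. The plan's own intervals.** Wald: p ± 1.96·√(p(1−p)/50). Exact: Clopper-Pearson.

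| Observed | Wald | Stated in B.10 | Exact |
|---|---|---|---|
| 35/50 (70%) | 57.3–82.7 | 57–83 | 55.4–82.1 |
| 40/50 (80%) | 68.9–91.1 | 69–91 | 66.3–90.0 |
| 45/50 (90%) | 81.7–98.3 | 82–98 | 78.2–96.7 |

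The stated figures reproduce as Wald. At 90% observed, the stated interval covers all of 94–97% but also reaches 12 points below 94% (94 − 82).

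**2. If a-DOT matched the benchmark.** At 47/50 the exact 95% interval is 83.5–98.7; at 48/50 it is 86.3–99.5. The lower limits are 94 − 83.5 = 10.5 and 96 − 86.3 = 9.7 points below the observed rates. The Wald interval at 47/50 is 0.94 ± 1.96·√(0.94·0.06/50) = 87.4–100.6, so it passes 100%.

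**3. Chance of meeting an illustrative rule.** Assume success means a lower limit above 84%, which is 10 points below 94%. Find the smallest qualifying count k, then P(X ≥ k) for X ~ Binomial(50, p).

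| Interval | Lower limit just failing | Lower limit just passing | k | p=94% | p=95% | p=97% |
|---|---|---|---|---|---|---|
| Exact 95% | 83.5 (47) | 86.3 (48) | 48 | 42% | 54% | 81% |
| Wilson 95% | 83.8 (47) | 86.5 (48) | 48 | 42% | 54% | 81% |
| Exact 90% | 82.6 (46) | 85.2 (47) | 47 | 65% | 76% | 94% |
| Wald 95% | 81.7 (45) | 84.5 (46) | 46 | 82% | 90% | 98% |

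**4. Two-sided equivalence at other assumed margins.** This is the probability that the exact 90% interval lies wholly within reference ± margin, with true SVR equal to the reference.

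| Margin | Ref 94% | Ref 95.5% | Ref 97% |
|---|---|---|---|
| ±5 points | 0% | 34% | 22% |
| ±10 points | 65% | 61% | 81% |
| ±15 points | 92% | 93% | 98% |

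For 80% power to hold the lower limit within 5 points, n ≈ p(1−p)(1.645+0.842)²/0.05². That is 0.0564·6.18/0.0025 ≈ 140 at 94% and 0.0291·6.18/0.0025 ≈ 72 at 97%, against the 50 available.

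**5. Reliability of the Wald option.** Coverage is the sum of Binomial(50, p) probabilities over the counts whose nominal 95% Wald interval contains p. It is 81%, 92%, 87% and 78% at p = 94%, 95%, 96% and 97%. Coverage moves unevenly between these points and touches about 95% just above 94%, but it is mostly well short of nominal. Wald's better chance in step 3 comes with this undercoverage.

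**The case against.** The strongest reply is that no formal equivalence test is claimed. The word appears in one clause of an expectation and can be read as meaning similar. B.9.5 calls the study a pilot, and B.10 aims at effect sizes for later trials. The a-DOT proportion with an interval is already planned, with an exact option, and the all-subject comparison is declared to be for feasibility. All of this stands, and it reduces the correction to wording. It does not remove the gap: the clause sits in a hypothesis of Aim 1, the power disclaimer covers only a-DOT against TAU, and nothing in B.10 links the a-DOT interval to the benchmark.

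Two stronger readings are tempting, and the documents do not support them.

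- A reader might infer that a non-significant difference from historical SVR will be taken as equivalence. B.10 names no test, p-value or decision rule for that comparison and gives its purpose as feasibility. Error rates for such a procedure would rest on an invented test and reference.
- A reader might infer that this design could not show equivalence at all. That fails at wider margins: at ±10 to ±15 points, step 4 gives 61–98%. The defect is that no margin is set. Sample size is a further obstacle only if the margin is narrow.

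**Conclusion.** The point holds as a gap between hypothesis and analysis. Aim 1 predicts equivalence of a-DOT SVR to registration-trial SVR; the plan supplies no margin, reference or criterion, and its one external comparison concerns a different group. As written, no result could properly be reported as equivalence.

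The size depends on assumptions that the documents do not settle. With a fixed benchmark of 94–97% and 50 evaluable subjects, power is 0–34% at ±5 points. For a lower limit above 84% at true SVR 94%, the chance is 42%, 65% or 82% according to the interval used, so the choice of interval alone could change the conclusion. Losses to follow-up would widen the intervals further.

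The consequence is limited to what may be claimed. The planned a-DOT estimate is itself sound once the Wald option is removed.

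**What to change.** 1. In Aim 1, replace the equivalence clause with an estimation statement: SVR in the a-DOT subjects will be estimated and set beside the cited 94–97%, and no equivalence claim will be made.
2. In B.10, keep the planned a-DOT SVR (n=50), name one interval (exact or Wilson 95%), drop Wald, and present the result beside 94–97%.
3. Keep the all-subject comparison as a descriptive feasibility summary only, and say which historical controls are meant.

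**Cost.** A few sentences are reworded; no subjects, visits or data are added. An equivalence claim is given up. The worked examples change slightly: in exact form 57–83% becomes 55–82%, 69–91% becomes 66–90%, and 82–98% becomes 78–97%.

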Adherence to Zepatier (continuous measure) will be determined as the amount of medication taken by each patient during the first 12 weeks will be expressed as a percentage (with a 0-100% range) of the target dose. Subjects will be classified as "adherent" if they receive at least 80% of the total dose of Zepatier. Subjects who receive less than 80% of the total dose of Zepatier will be classified as "non-adherent." Analyses using self-reported adherence will also be conducted. Self-report is more accessible to clinicians than pill count, and there is added value in performing analogous analyses using the self-report measure.

Because adherence will be measured two ways (pill counts and self-report) *concordance correlation coefficients* will be calculated and performed to evaluate agreement between the measures. We will also test if the means of the two measurements are equal. Because adherence will be measured monthly, mixed-effects linear models for repeated measures that account for within-subject correlation will be used. In addition, we will examine the adherence data using a dichotomous cut-off (adherence \geq 80%), and determine the proportion of subjects who were sometimes, always, or never adherent during the 12-week treatment period. To this end, separate analyses will be performed for pill count and self-report adherence data.

For subjects randomized to the a-DOT arm, association between active drug use during treatment and the continuous adherence will be tested using Student's t or Wilcoxon signed rank test, depending on normality of the data. Bivariate analysis of dichotomous adherence data with categorical variables will be performed with chi-square and Fisher exact tests. We will conduct multivariate logistic regression analyses based on findings from the univariate analysis, but recognize that our modest sample size will limit such models.

Based on our pilot data, if we conservatively assume that 80% of subjects in the a-DOT will achieve \geq 80% adherence (v. 50% in the TAU arm), we will have $>$ 80% power to find a statistically significant difference. With the application of mixed-effects logistic regression to the repeatedly measured binary adherence outcome, power will be greater than 80% no matter how large the within-subject outcome correlation or intraclass correlation (ICC).

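### Aim 4 asks about virologic outcomes by drug use but has no such analysis, and its hypothesis of no association with adherence is paired only with tests for a difference

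*Combined protocol and SAP*

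**What the plan says.** Aim 4, in the numbered aims before section B, reads "To determine the impact of ongoing drug use (cocaine, opiates, or benzodiazepenes) and on HCV virologic outcomes in subjects receiving Zepatier by aDOT". The sentence after it gives the hypothesis: "We hypothesize that ongoing drug use during HCV treatment will not be associated with adherence in subjects randomized to a-DOT".

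Section B.10 says that, for subjects randomized to a-DOT, "association between active drug use during treatment and the continuous adherence will be tested" by a t or Wilcoxon test. It adds "Bivariate analysis of dichotomous adherence data with categorical variables will be performed with chi-square and Fisher exact tests", then logistic regression built on the univariate results. The power text for drug use, stated "with 80% power and 5% significance level in a two-tailed test", concerns the percentage adherent: 71% in the favorable group against 41% in the unfavorable one.

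SVR appears in B.10 as a proportion with a confidence interval "of subjects randomized to aDOT arm (n=50) who achieve SVR", and for all subjects against historical controls. Apart from these adherence analyses, B.10 uses drug use only in the check of baseline balance and possible covariate adjustment. Table 3 (section B.9.2) lists viral load at weeks 0, 4, 8 and 12 and follow-up weeks 4 and 12, and urine toxicology at weeks 0, 4, 8 and 12.

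**The concern.** There are two gaps. First, the outcome that Aim 4 names is virologic, yet no planned analysis relates drug use to viral load or SVR. Followed as written, the trial would not answer that part of the aim.

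Second, the adherence hypothesis is one of no association, and the only tools given are tests for a difference. There is no margin, no interval criterion and no rule for a non-significant result. Failing to reject shows only that the data did not exclude zero difference; it does not show that the difference is small. At stake is a statement that active drug use does not matter for adherence under a-DOT, made from data that may be compatible with a sizeable effect.

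**Working it through.** **Coverage.** Setting the aim beside B.10:

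| Drug use against | In Aim 4 | Analysis in B.10 |
|---|---|---|
| Continuous adherence | hypothesis | t or Wilcoxon test |
| Adherence of at least 80% | hypothesis | chi-square or Fisher; logistic regression |
| SVR or viral load | stated objective | none |

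**The plan's own figures.** The Wald intervals for SVR at n = 50 reproduce (57–83%, 69–91%, 82–98%). The detectable difference of 71% v 41% gives an odds ratio of (0.71/0.29)/(0.41/0.59) = 3.52, against 3.55 in the plan, which is within rounding. No sample size is given with it. With 50 subjects, exact two-sided Fisher power for 71% v 41% is 0.51 at 25:25 and 0.45 at 35 non-users to 15 users. That statement therefore cannot serve as 80% power for the a-DOT subjects of Aim 4.

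**Inputs for the miss rates.**
- n = 50 a-DOT subjects, two-sided 5% (B.10).
- Split between users and non-users: not given for this trial. 25:25 is an assumption; 35:15 uses the 30% on-treatment use reported in section B.1.3.
- SD of adherence: 12 (observed-therapy arm) and 20 (usual-treatment arm) in the earlier study (B.10); 16.5 = √[(12² + 20²)/2].
- Gap of 10 points: 87% − 77% in that study.

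**Adherence of at least 80%.** Probability that Fisher's test is non-significant, by exact enumeration of the two binomials:

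| True rates, non-users v users | 25:25 | 35:15 |
|---|---|---|
| 90% v 70% | 70% | 63% |
| 80% v 60% | 77% | 71% |

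With 80% adherent in both groups, the 95% CI half-width for the difference is 1.96 × √[0.8 × 0.2 × (1/25 + 1/25)] = 22 points. At 35:15 it is 24 points.

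**Continuous adherence.** At 25:25, SE = SD × √(2/25), the half-width is 2.01 × SE, and the miss rate for a true 10-point gap comes from the noncentral t with 48 df and noncentrality 10/SE.

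| SD | SE | Noncentrality | Miss rate | CI half-width |
|---|---|---|---|---|
| 12 | 3.39 | 2.95 | 18% | 6.8 |
| 16.5 | 4.67 | 2.14 | 44% | 9.4 |
| 20 | 5.66 | 1.77 | 59% | 11.4 |

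At SD 12 and 35:15 the miss rate is 25%. Also at SD 12, if there is truly no difference, the whole 95% CI falls within ±10 points about 65% of the time at 25:25 and 51% at 35:15 (simulation).

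**SVR by drug use.** At the 94–97% SVR cited in the introduction, expected failures among 50 are 50 × 0.03 = 1.5 to 50 × 0.06 = 3. Fisher power at 25:25 is 0.07 for 95% v 85% and 0.20 for 95% v 80%. A comparison can only be descriptive.

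**The case against.** Several points on the other side stand.

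- A reader might infer that the aim and its hypothesis contradict each other. The stray conjunction before "on HCV virologic outcomes in subjects receiving Zepatier by aDOT" suggests that a first outcome dropped out of the sentence, and adherence is the likely one. The hypothesis would then cover one of two outcomes. The virologic outcome still has no analysis.
- A reader might infer that the plan will report non-significance as proof of no association. No section says how such a result will be read. B.10 admits that the modest sample limits its multivariate models, and B.9.5 calls the study a pilot. What the text does show is that the planned tests cannot supply support for the hypothesis.
- A reader might infer that the test would usually miss a real effect. For continuous adherence this depends on the SD. The observed-therapy SD of 12 is arguably the closest to a-DOT, and there a 10-point gap is missed only 18% of the time at 25:25.
- A reader might take All in Table 3 to mean all arms and ask for the same comparison in TAU. That column is headed by aim and hypothesis, so the entry means all aims. Aim 4 is limited to a-DOT subjects, and a TAU comparison would add an objective.
- The missing SVR analysis could only be descriptive, and this is the last-listed aim of a pilot. That limits the weight of the point but does not remove it: a stated objective should have an analysis.

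**Conclusion.** The point holds in limited form. The virologic part of Aim 4 has no analysis; that rests on the text alone. The adherence part states a null hypothesis that difference tests in about 50 subjects cannot support; that is a matter of logic, and the sample size sets how much it matters. For adherence as a yes/no measure, true 20-point differences go undetected in roughly 63% to 77% of trials. For continuous adherence, a 10-point gap at 25:25 is missed 18% to 59% of the time over SDs of 12 to 20. The splits, true rates and SDs are assumptions, taken from the documents where they offer a value. The point does not concern the main a-DOT v TAU comparison. It should be corrected because it changes what Aim 4 can conclude.

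**What to change.** 1. Complete the Aim 4 sentence so that it names every intended outcome. Add to B.10: SVR in a-DOT subjects with and without a positive on-treatment urine toxicology (weeks 4, 8 or 12), with the difference and an exact 95% CI, labelled descriptive because only about 1.5 to 3 failures are expected.
2. Replace the hypothesis of no association by estimation: the user minus non-user difference in adherence with its 95% CI. Conclude no meaningful association only if the whole interval lies inside a margin that the investigators state in advance; otherwise report not determined.

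The cost is protocol and analysis wording. Viral load and toxicology are already scheduled in Table 3, and no subjects are added. The downside is that Aim 4 may end as not determined. At 25:25 the interval extends about 7, 9 or 11 points either side at SD 12, 16.5 or 20, so a 10-point margin, for example, is attainable at the smallest SD but unlikely to be met at the largest.
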